13.4 End of Study Definition

Please refer to Section [4.5](#) for the definition of the end of the study. Module 1 will be considered complete once the last participant enrolled in this Module undergoes a 30-Day Safety Follow-up visit, or if the treating site has confirmed the SFU visit will not be performed. Participants still receiving clinical benefit from AZD4573 and continuing treatment after the data cut-off for the primary analysis will be considered to have completed Module 1 on the date AZD4573 is permanently discontinued.

In addition, the study may be terminated, or individual centres closed at the discretion of AstraZeneca (please refer to [Appendix A 9](#)). AstraZeneca may also terminate the module prematurely if concerns for safety arise within this study or in any other study with AZD4573 and/or acalabrutinib.

The data cut-off for the primary analysis for each expansion subgroup will occur approximately 6 months following last participant first dose in the expansion subgroup or when 75% of participants have progressed or died in the cohort, whichever occurs first.

The results from Module 1 will be reported to Regulatory Authorities within one year of the end of module.

14 STUDY POPULATION – MODULE 1

Prospective approval of protocol deviations to recruitment and enrolment criteria, also known as protocol waivers or exemptions, is not permitted.

Participants must meet the inclusion and exclusion criteria of both the core and module protocol. Where there are differences in stringency or cut-off values, the specific module takes precedence. For example, if haematological medication parameters are stricter in the module than in the core, the Investigator should adhere to the module criteria.

14.1 Inclusion Criteria

Each participant should meet all the inclusion criteria (and none of the exclusion criteria) for this study in order to be assigned to a study cohort. Under no circumstances can there be exceptions to this rule.

NOTE: This Module will be enrolling participants with DLBCL or MZL only.

For inclusion in the study, participants must fulfil all of the following criteria:

- 1 Participants must meet the eligibility criteria described in Section 5.1.
- 2 Participants with histologically confirmed, r/r DLBCL or r/r MZL, for whom a clinical study is the best option (in the opinion of the Investigator) for next treatment based on response and/or tolerability to prior lines of therapy.

PART A

- Participants with r/r DLBCL, including subtypes such as DLBCL not otherwise specified [NOS], high-grade B-cell lymphoma [HGBCL], primary mediastinal large B-cell lymphoma [PMBCL], or large B-cell lymphoma transformed from indolent B-cell lymphomas (including but not limited to Richter Syndrome, transformed Follicular Lymphoma, transformed MZL), or r/r MZL:
 - Diagnosis must be confirmed by biopsy and be immunohistologically characterised.
 - For participants with DLBCL, cell of origin subtype shall be characterised locally and tumour tissue must also be available for sending to AstraZeneca for central cell of origin/pathology testing (see below).

All participants in Part A (dose setting) must consent to and provide archival tumour specimens, preferably in the form of a formalin-fixed paraffin embedded block (tissue derived from the diagnostic tumour or a metastatic site). If this is not possible, an appropriate number of slides of freshly prepared unstained 5-micron sections from the archival tumour block may be provided as defined in the study Laboratory Manual. Archival tumour specimens must be obtained within 24 months before the first dose of IP. If archival material is unavailable or unsuitable for use, participants must consent to and undergo a fresh tumour biopsy during the screening period. A fresh biopsy is strongly encouraged and preferred, however, a participant will be enrolled based on the prior pathology report.

PART B

Participants with r/r de novo DLBCL, GCB or non-GCB subtype:

- Must have received SoC first-line therapy.
- Diagnosis must be confirmed by biopsy and cell of origin subtype characterised locally prior to enrolment and DLBCL be immunohistologically characterised.
- A newly obtained tumour biopsy is strongly encouraged and preferred at Screening to confirm cell of origin status and determine DLBCL subtype. The participant will be enrolled based on a prior pathology report.

A recent biopsy that was taken as part of SoC prior to screening consent for this study is acceptable if no treatment was administered between the biopsy and the first dose of study treatment, and the biopsy was taken within 60 days prior to receiving the first dose.

If fresh biopsy is not feasible/safe per local interventional radiologist or biopsy attempt fails to retrieve viable lymphoma tissue the participant can still be considered for the study (Part B) after discussion with the Sponsor's medical monitor.

- 3 Presence of radiographically measurable lymphadenopathy or extranodal lymphoid malignancy (according to the Lugano criteria [[Cheson et al 2014](#)]).
- 4 Participants must have failed at least two prior therapies for the treatment of current disease. Participants shall not be eligible for curative treatment options, and have no standard therapy available (including CAR-T cell therapy).
- 5 Adequate haematologic function at Screening, as defined in [Table 9](#):
 - (a) No growth factor support within 14 days prior to the date of the screening laboratory assessment.
 - (b) No transfusions within 7 days prior to the date of the screening laboratory assessment.

Table 9 Criteria for Adequate Haematological Function

Category	Parameter	Value
Haematologic	Haemoglobin	≥ 8.0 g/dL
	Absolute neutrophil count	≥ 1000 cells/mm ³ (1.0×10^9 /L)
	– Platelet count	$\geq 75,000$ cells/mm ³ (75×10^9 /L) without bone marrow involvement
		$\geq 50,000$ cells/mm ³ (50×10^9 /L) with bone marrow involvement

- If indicated, transfusions or growth factors can be administered during the screening period, but such cases of deterioration of haematological function must be discussed with the Medical Monitor, to confirm start of study treatment.

- 6 **Optional** tumour biopsy on study: Participants are also encouraged to consent to and undergo an optional tumour biopsy at disease progression to support correlative biomarker studies.
- 7 All participants must be willing and able to provide mandatory baseline bone marrow biopsy/aspirate.

14.2 Exclusion Criteria

Participants are excluded from the study if any of the following criteria apply:

- 1 Participants must comply with the exclusion criteria described in Section [5.2](#).

- 2 Current refractory nausea and vomiting, malabsorption syndrome, disease significantly affecting gastrointestinal function, resection of the stomach, extensive small bowel resection that is likely to affect absorption, symptomatic inflammatory bowel disease, partial or complete bowel obstruction, or gastric restrictions and bariatric surgery, such as gastric bypass.
- 3 Prior use of standard anti-lymphoma therapy or radiation therapy within 14 days of receiving the first dose of study treatment.
- 4 Requires treatment with strong CYP3A inhibitors or inducers (please refer to [Appendix F](#) for a list of strong inhibitors and inducers of CYP3A).
- 5 Requires treatment with proton-pump inhibitors (eg, omeprazole, esomeprazole, lansoprazole, dexlansoprazole, rabeprazole, or pantoprazole). Participants receiving proton-pump inhibitors who switch to H₂-receptor antagonists or antacids are eligible for enrolment to this study (see Section [15.11.4](#)).
- 6 Serologic status reflecting active hepatitis B or C infection:
 - (a) Participants who are anti-HBc positive and who are surface antigen negative will need to have a negative PCR result before enrolment. Those who are hepatitis B surface antigen positive or hepatitis B PCR positive will be excluded.
 - (b) Participants who are hepatitis C antibody positive will need to have a negative PCR result before enrolment. Those who are hepatitis C PCR positive will be excluded.
- 7 Active Cytomegalovirus (CMV) infection (positive CMV immunoglobulin M [IgM] and positive PCR result).
- 8 Requires or receiving therapeutic anticoagulants, with the exception of short-acting heparins, within 7 days of first dose of study treatment. Novel oral anticoagulants are allowed except for the initial high dose treatment period.
- 9 Participants on dual antiplatelet and therapeutic anticoagulant therapy (eg, aspirin and therapeutic doses of low molecular weight heparin).
- 10 Requires or receiving anticoagulation with warfarin or equivalent vitamin K antagonists.
- 11 History of or ongoing confirmed progressive multifocal leukoencephalopathy (PML).

14.3 Lifestyle Considerations

Please refer to Section [5.3](#), in addition to Section [14.3.1](#).

14.3.1 Meals and Dietary Restrictions – Module 1

Acalabrutinib is best taken with water and can be taken with or without food. As acalabrutinib is metabolised by CYP3A, participants should be strongly cautioned against using herbal remedies or dietary supplements (in particular, St John's wort, which is a potent CYP3A inducer).

Otherwise, participants should maintain their regular diet unless modifications are required to manage an AE such as diarrhoea, nausea, or vomiting.

14.4 Screen Failures

Please refer to Section [5.4](#).

15 STUDY INTERVENTION – MODULE 1

Study intervention is defined as any investigational intervention(s), marketed product(s), placebo, or medical device(s) intended to be administered to a study participant according to the study protocol.

15.1 Study Intervention(s) Administered

15.1.1 Investigational Products

AZD4573 will be administered as an absolute (flat) dose, 2-hour (\pm 15 minutes) IV infusion once weekly, at least 5 days apart, in combination with orally administered acalabrutinib 100 mg twice daily continuously. For both Part A and Part B of this study, Cycle 1 consists of 5 weeks, with a dose ramp up. Subsequent cycles are 21 days (3 weeks) with once-weekly dosing of AZD4573 in combination with acalabrutinib 100 mg twice daily continuously.

AZD4573 and acalabrutinib will be supplied by AstraZeneca. CCI

Detailed

information on the drug products and administration guidelines are in the AZD4573 Handling Instructions and acalabrutinib participant leaflet.

Labels will be prepared in accordance with Good Manufacturing Practice and local regulatory guidelines and will be translated into the local language. The labels will fulfil Good Manufacturing Practice Annex 13 requirements for labelling.

All IPs should be kept in a secure place under appropriate storage conditions. The IP label on the vial (AZD4573) or bottle (acalabrutinib) specifies the appropriate storage conditions.

Participants enrolled in this study module will receive acalabrutinib in combination with AZD4573, in accordance with the dosing scheme provided in Section 13.1. Acalabrutinib is intended to be administered orally every day, twice daily with approximately 240 mL of water and can be administered without regard to food. Doses should be administered 12 hours apart (a window of \pm 1 hour is allowed) at approximately the same times each day. Treatment with AZD4573 and acalabrutinib, in Part A and Part B, may be continued until disease progression, an unacceptable drug-related toxicity occurs as defined in the protocol, or the participant withdraws or is withdrawn from the study for other reasons. The acalabrutinib capsules should be swallowed intact. Participants should not attempt to open capsules or dissolve in water. If vomiting occurs after taking acalabrutinib, the participant should not retake acalabrutinib until the next scheduled dose.

On the day of PK collection, acalabrutinib capsules should be brought to site by the participant and taken within 5 minutes before initiation of AZD4573. The actual date and time of AZD4573 and acalabrutinib dosing will be recorded.

Table 10 Investigational Products

Intervention Name	AZD4573	Acalabrutinib
Type	Drug	Drug
Dose Formulation	Concentrate for solution for infusion	Capsules
Unit Dose Strength(s)	1.5 mg/mL	100 mg
Dosage Level(s)	1.5 mg – 12.0 mg	100 mg BID
Route of Administration	IV infusion	Oral
Use	Experimental	Experimental
IMP and NIMP	IMP	IMP
Sourcing	Provided centrally by AstraZeneca	Provided centrally by AstraZeneca
Packaging and Labelling	Study Intervention will be provided in vials. Each vial will be labelled as required per country requirement	Study Intervention will be provided in bottles. Each bottle will be labelled as required per country requirement
Current/Former Name(s) or Alias(es)	AZD4573/ AZ13810325	Acalabrutinib/ACP-196/Calquence

Abbreviations: BID = twice daily; IMP = investigational medicinal product; IV = intravenous; NIMP = non-investigational medicinal product.

If an acalabrutinib dose is not taken within the allowed window, it can be taken up to 2 hours after the scheduled time with a return to the normal schedule the same or following day. If it has been > 2 hours, the dose should not be taken, and the participant should take the next dose at the next scheduled time. The missed dose will not be made up and must be returned to the site at the next scheduled visit. If a participant needs to take a dose earlier than scheduled, the participant can take the dose up to 2 hours earlier than the scheduled time except on scheduled site visit days. Participants should make every reasonable effort to take the acalabrutinib on time. Guidance on co-administration of acalabrutinib with agents that affect gastric pH is provided in Section 15.11.

15.2 Starting Dose, Dose-Escalation Scheme, and Stopping Criteria

The starting dose of AZD4573 selected for this study is 3 mg (Week 1 of Cycle 1) for the initial dose of the ramp-up period in the dose setting cohorts. The initial target dose following the ramp up is 9 mg (dose level 1). The starting and target dose were based on clinical data from an ongoing Phase I FTIH study of AZD4573 monotherapy (D8230C00001, see Section 13.3). The initial starting dose of AZD4573 was selected based on the safety information for AZD4573 monotherapy in the ongoing first-in-human study (Study D8230C00001) and is at least one dose level below the RP2D for monotherapy.

A study-specific SRC in accordance with its charter, will be responsible for providing ongoing safety surveillance of the study, with regularly scheduled reviews of safety, PK, and other relevant data (see Section 18.6). This committee will be responsible for making recommendations for dose escalation or dose de-escalation recommendations, including recommendations on opening cohorts for backfill, as well as making recommendations regarding further conduct of the study.

This study includes intra-patient dose escalation (ie, ramp-up dosing) in each cohort to reach the target dose level as a safety precaution. The intra-patient dose-escalation scheme and/or dose schedule for each cohort may be modified based on the safety and PK findings of a previous dose level.

For each new dose level, the initial dose setting cohort will require at least 3 evaluable participants and a maximum of 6. A recommendation about the dose level for each next cohort will be made by the SRC, guided by rules based on the mTPI-2 design (Guo et al 2017) with a 30% target DLT rate ($\pm 5\%$) for MTD (see Table 11): dose escalation (E), stay (S) at the current dose, de-escalation (D), or de-escalation and current dose is unsafe (DU).

Table 11 Decision Rules Based on mTPI-2 for Dose Escalation

Number of DLTs	Number of DLT-Evaluable Participants Treated at Current Dose Level									
	n = 1	n = 2	n = 3	n = 4	n = 5	n = 6	n = 7	n = 8	n = 9	
0	S ^a	S ^a	E	E	E	E	E	E	E	
1	S ^b	S ^b	S	S	E	E	E	E	E	
2		DU	D	D	D	S	S	S	E	
3			DU	DU	D	D	D	D	S	
4				DU	DU	DU	D	D	D	
5					DU	DU	DU	DU	DU	
6						DU	DU	DU	DU	

Number of DLTs	Number of DLT-Evaluable Participants Treated at Current Dose Level								
7							DU	DU	DU
8								DU	DU
9									DU

^a Changed from E to S as a minimum of 3 evaluable participants are needed to make a dose-escalation decision.

^b Changed from D to S as a minimum of 3 evaluable participants are needed to make a dose de-escalation decision.

Note: E = escalate to the next higher dose level, S = stay at the current dose level, D = de-escalate to the next lower dose level; DU = de-escalate to the previous lower dose and the current dose will never be used again due to unacceptable toxicity.

Abbreviations: D = de-escalation; DLT = dose-limiting toxicity; DU = dose unsafe; E = escalation; mTPI-2 = modified toxicity probability interval; S = stay.

A dose level will be considered as having unacceptable toxicity, with no additional participants enrolled at that dose level and above, if it has an estimated 95% or more probability of exceeding the 30% target DLT rate. Otherwise, dose escalation is terminated when the prespecified maximum target dose is reached (AZD4573 12 mg).

If a stay decision is made, additional participants may be enrolled (usually in cohorts of 2 to 6 participants) up to a maximum of 9 total evaluable participants for a given dose level and a maximum of 24 evaluable participants for dose setting (ie, a maximum of 9 evaluable participants at each of two dose levels and 6 evaluable participants at the third dose level).

At any timepoint during the study, the occurrence of a fatal AE deemed related to study therapy (after full etiological work-up and in discussion with the SRC) will result in accrual stoppage and a comprehensive review of safety. In addition, potential safety signals arising from Grade ≤ 4 treatment-related AEs will be reviewed in the context of the overall benefit/risk. On review any event deemed to adversely affect overall benefit risk will trigger an ad hoc SRC for comprehensive safety review.

In the case of PHL, if bilirubin remains elevated (compared to baseline) at 96 hours (-2/+12 hours) after the start of the infusion, the participant must be discontinued from the study and biochemistry followed until resolution. The Sponsor must be notified immediately.

Part A participants, including backfills, receiving the RP2D of AZD4573 + acalabrutinib combination therapy beyond the Cycle 1 DLT-assessment period and Part B participants receiving AZD4573 + acalabrutinib combination therapy from their first Cycle 1 dose onwards will be monitored for safety using the same DLT criteria employed during dose setting. If, on an ongoing basis, $> 30\%$ of participants experience any safety events that meet the criteria of a DLT or $> 30\%$ of participants discontinue study treatment due to TLS, enrolment into the expansion cohorts may be paused for evaluation of the study data by the

SRC. Following SRC review additional monitoring may be implemented and/or enrolment and dosing may resume at a lower combination dose level or a modified schedule as defined in the dose setting phase. Further details will be provided in the Medical Monitoring Plan.

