- A delay in dosing of more than approximately 7 consecutive days (\pm 2 days), in other words, more than 1 missed dose, due to a dose-related toxicity occurring during the 5-week DLT-assessment period (toxicity that is clearly and directly related to the primary disease or to another aetiology is excluded from this definition).

Isolated elevations of transaminases:

- Grade 3 elevations ($\geq 5 \times$ ULN) in ALT or AST, without concomitant elevation in total bilirubin $> 2 \times$ ULN, that do not return to Grade 1 within 7 days from start of dosing.
- Grade 4 elevations in ALT ($\geq 20 \times$ ULN) of any duration irrespective of total bilirubin.
- Grade 4 elevations in AST ($\geq 20 \times$ ULN) without concomitant elevation in ALT $\geq 20 \times$ ULN or total bilirubin $\geq 2 \times$ ULN that do not return to Grade 1 within 7 days from start of dosing.

Elevations in transaminases with concomitant elevation of bilirubin (Potential Hy's Law [PHL]):

- Elevations in ALT or AST $\geq 3 \times$ ULN with concomitant elevation in total bilirubin $\geq 2 \times$ ULN where bilirubin does not return to meet initial eligibility criteria within 72 hours of onset or 96 hours of start of dosing (-2/+12 hours) whichever is the sooner, and/or ALT or AST do not return to meet initial eligibility criteria within 7 days post start of dose.
- Elevations in ALT or AST $\geq 3 \times$ ULN with concomitant elevation in total bilirubin $\geq 2 \times$ ULN and INR $> 1.5 \times$ ULN (or $> 1.5 \times$ baseline, if elevated at baseline) of any duration.
- Elevations in ALT or AST $\geq 3 \times$ ULN with concomitant elevation in total bilirubin $\geq 2 \times$ ULN of any duration if associated with symptoms or signs of liver impairment (eg, appearance of fatigue, nausea, vomiting, right upper quadrant pain or tenderness, fever, rash, and/or eosinophilia $> 5\%$).

Any of the following haematological toxicities:

- CTCAE Grade 4 neutrophil count decrease lasting > 7 days, despite growth factor support.
- Grade ≥ 3 febrile neutropenia (absolute neutrophil count [ANC] $< 1.0 \times 10^9/L$, fever $> 100.9^{\circ}\text{F}$ [or $> 38.3^{\circ}\text{C}$]) of any duration despite supportive care.
- CTCAE Grade 4 thrombocytopenia lasting more than 7 days or Grade ≥ 3 thrombocytopenia, of any duration, associated with \geq Grade 2 bleeding.

- CTCAE Grade 4 anaemia despite transfusion.

Any Tumour Lysis Syndrome meeting the following criteria:

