Grade 4^c Isolated AST elevation $\geq 20 \times$ ULN without concomitant elevation in ALT $\geq 20 \times$ ULN or TBL $\geq 2 \times$ ULN	1st occurrence If recovered to Grade ≤ 1 or baseline level within 7 days of the start of the infusion allow rechallenge at same dose level 2nd occurrence If recovered to Grade ≤ 1 or baseline level within 7 days of the start of the infusion allow rechallenge with 1 dose level reduction 3rd occurrence Discontinue AZD4573	Withhold or continue acalabrutinib (at Investigator discretion, after discussion with the Medical Monitor). To prevent disease progression, monitor disease parameters closely. Monitor ALT, AST, ALP, and bilirubin at least 1x per week. After 7 days if hepatic enzymes appear to be improving and acalabrutinib was withheld, restart acalabrutinib at current dose level at the 1st occurrence and with 1 level dose reduction at the 2nd occurrence . Discontinue acalabrutinib at the 3rd occurrence .
Concurrent elevations in ALT, AST, or bilirubin (Please also refer to Appendix E for actions to be taken in the event of PHL)		
ALT or AST $\geq 3 \times$ ULN with TBL $\geq 2 \times$ ULN (Potential Hy's Law) AND INR $\geq 1.5 \times$ ULN (or $\geq 1.5 \times$ baseline if elevated at baseline) of any duration	Discontinue AZD4573.	Discontinue acalabrutinib.
ALT or AST $\geq 3 \times$ ULN with the appearance of fatigue, nausea, vomiting, right upper quadrant pain or tenderness, fever, rash, and/or eosinophilia $> 5\%$	Discontinue AZD4573.	Discontinue acalabrutinib.
ALT or AST $\geq 3 \times$ ULN and TBL $\geq 2 \times$ ULN where TBL does not return to baseline level within 96 hours (-2/+12 hours) from start of dose and/or AST or ALT do not return to baseline level within 7 days from start of dose	Discontinue AZD4573.	Discontinue acalabrutinib.

Event ^a	Action	
	AZD4573	Acalabrutinib
Grade 3 elevation ($\geq 5 \times$ ULN) in ALT or AST with TBL elevation above baseline level or ULN, but $< 2 \times$ ULN that do not return to baseline level within 7 days	Discontinue AZD4573.	Discontinue acalabrutinib.

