ALT and AST $\geq 3 \times$ ULN with concomitant TBL $\geq 2 \times$ ULN, NO increase in INR $\geq 1.5 \times$ ULN (or $1.5 \times$ baseline), and NO fatigue, nausea, vomiting, right upper quadrant pain or tenderness, fever, rash, and/or eosinophilia $> 5\%$	If recovered to Grade ≤ 1 or baseline level within 96 (-2/+12) hours, rechallenge at same dose level ^c	Withhold acalabrutinib until recovered. Once recovered, restart acalabrutinib at same dose.

^a Adverse reactions are graded using National Cancer Institute CTCAE version 5.0. All grades refer to CTCAE grading except for TLS, which uses the Howard modification of Cairo-Bishop criteria (Howard et al 2011).

^b Elevations in ALT or AST are considered isolated if bilirubin remains below Grade 1, and elevations in bilirubin are considered isolated if ALT and AST remain below Grade 1.

^c Participants who are considered for rechallenge in the event of Grade 4 transaminase increases or PHL must discuss possible risk of hepatotoxicity with the treating physician, who will document this discussion and participant agreement for continued treatment in the medical records.

Note: Adequate supportive therapy as per institutional guidelines should be given for all toxicities.

Abbreviations: ALP = alkaline phosphatase; ALT = alanine aminotransferase; AST = aspartate aminotransferase; CTCAE = Common Terminology Criteria for Adverse Events; INR = international normalised ratio; PHL = Potential Hy's Law; TBL = total bilirubin; ULN = upper limit of normal.

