15.12.1 Retreatment Criteria

Retreatment is defined as the first dose of study drug after a significant period of intentional pause in study drug treatment (other than missed doses, eg, study treatment put on hold until resolution of COVID-19).

Retreatment criteria (criteria to be met before participant restarts study drug infusions [and capsules, as applicable]):

All participants:

- 1 Participant has recovered from all treatment-related non-haematological toxicity to CTCAE Grade ≤ 2 .
- 2 Recovery of neutrophils $\geq 1000/\mu\text{L}$ and platelets $\geq 50,000/\mu\text{L}$.
- 3 Participant has recovered from all hepatic toxicity events within the timeframes described in Table 14 above. If biochemical changes in transaminase(s) and total bilirubin are consistent with the definition of HL, the participant may continue to receive study drug

only if all abnormalities have resolved within the timeframes specified in [Table 14](#) above, there are no symptoms of liver injury and INR has not increased above $1.5 \times$ ULN (or $1.5 \times$ baseline). In these circumstances the participant must be made aware of the unknown potential for liver damage with continued exposure to AZD4573 prior to retreatment. Documentation of continued consent is required.

- 4 Recovery of uric acid to $<$ ULN.
- 5 Recovery of changes in uric acid, potassium, phosphorus, creatinine or calcium, or symptoms suggestive of TLS as defined in [Table 13](#).
- 6 In case of any new deterioration in laboratory values, not fulfilling eligibility criteria and deemed as clinically significant by the Investigator, the Medical Monitor must be contacted to discuss whether AZD4573 dosing can be continued.

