If bilirubin fails to resolve within 96 hours (-2/+12 hours) or transaminases fail to resolve within 7 days, or if the event is associated with significant clotting abnormality or clinical symptoms of liver disease, study treatment must be permanently discontinued (the participant remains on study for the 30-day SFU and long-term follow-up [LTFU] visits), and the event must be immediately communicated to AstraZeneca.

For guidance on treating liver toxicity, please refer to [Table 14](#) of this protocol.

During the course of the study the Investigator will remain vigilant for increases in liver biochemistry. The Investigator is responsible for determining whether a participant meets PHL criteria at any point during the study.

Please refer to [Appendix E](#) for the process to be followed to identify and appropriately report cases of PHL. It is not intended to be a comprehensive guide to the management of elevated liver biochemistries.

The Investigator will participate, together with the Medical Monitor, in review and assessment of PHL events to agree whether HL criteria are met. HL criteria are met if there is no alternative explanation for the elevations in liver biochemistry.

The Investigator is responsible for recording data pertaining to PHL/HL cases and for reporting AEs and SAEs according to the outcome of the review and assessment in line with standard safety reporting processes.

Regarding the hepatic toxicity events encountered to date with AZD4573, it has been observed that while the biochemical changes of increased transaminase with concomitant elevation in bilirubin seen in some participants could be classified as HL by its strict definition, they do not follow a pattern that is consistent with true HL predictive of hepatic injury, and are therefore 'PHL' cases. The events are rapidly resolved and to date have not led to any clinical sequelae or lasting hepatic injury. Repeated dosing with AZD4573 following these events has demonstrated that there is no consistent pattern of recurrence and no consistent increase in severity of the events if they do recur.

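### For one form of potential Hy's Law, Module 1 both requires a permanent stop and allows same-dose rechallenge, and it disagrees on whether the stop ends treatment or study participation

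*Protocol*

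**What the plan says.** Three places in Module 1 set the action for potential Hy's Law (PHL) by what bilirubin has done at 96 hours.

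- **Section 15.2.** If bilirubin is still "elevated (compared to baseline) at 96 hours (-2/+12 hours) after the start of the infusion, the participant must be discontinued from the study". The same sentence asks for biochemistry to be followed until resolution, and the next one for immediate notification of the Sponsor.
- **Section 15.12, Table 14, stop row.** Entry is ALT or AST at least 3 x ULN with bilirubin at least 2 x ULN. Both drugs are discontinued in the case "where TBL does not return to baseline level within 96 hours (-2/+12 hours) from start of dose", or if transaminases are not back to baseline within 7 days.
- **Section 15.12, Table 14, rechallenge row.** Entry is ALT and AST at least 3 x ULN with bilirubin at least 2 x ULN, no INR rise and none of the listed symptoms. On recovery to Grade 1 or lower, or to "baseline level within 96 (-2/+12) hours, rechallenge at same dose level". Acalabrutinib is withheld and restarted at the same dose once the event has recovered.

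Two further places refer to recovery without giving a level. Section 15.12.1 lets a participant continue "only if all abnormalities have resolved within the timeframes specified in" Table 14. Section 17.1.10.9 says that if bilirubin does not resolve within 96 hours, "study treatment must be permanently discontinued (the participant remains on study for the 30-day SFU and long-term follow-up [LTFU] visits").

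**The concern.** A stopping rule for suspected drug-induced liver injury should lead every site to the same action. Here a participant whose bilirubin has fallen to Grade 1 but not to baseline is covered by a mandatory stop and by a permission to re-dose at the same level. Two investigators could each follow the protocol and do opposite things. One error exposes a participant to a further dose that the stopping rule forbids. The other permanently ends treatment for someone whom the dose-modification table would let continue.

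The second disagreement is about what ends. Taken literally, removal from the study under Section 15.2 also drops the long-term follow-up visits that Section 17.1.10.9 keeps. It would also drop the scans that Section 17.4.2 continues until progression in participants who stop treatment for another reason.

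**Working it through.** No figure in the plan needs reproducing. The check sets the rules side by side and applies them to one case.

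**Step 1: do the two Table 14 rows overlap?** The stop row needs ALT or AST at least 3 x ULN; the rechallenge row needs both. Both rows need bilirubin at least 2 x ULN. If both transaminases are raised, then at least one is, so everyone who enters the rechallenge row also meets the liver-value entry condition of the stop row. The rows are not alternatives.

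**Step 2: bilirubin level required at 96 hours.** Let *b* be baseline bilirubin in multiples of ULN, in a participant without Gilbert's syndrome. Table 14 itself puts Grade 1 bilirubin at no more than 1.5 x ULN.

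- Section 15.2: stop if bilirubin is above *b*.
- Stop row: stop if bilirubin is above *b*.
- Rechallenge row: restart if bilirubin is at or below 1.5, or at *b*.

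The rules conflict whenever *b* < bilirubin ≤ 1.5, a band of width 1.5 − *b*. With *b* = 0.6 the width is 1.5 − 0.6 = 0.9 x ULN. With *b* = 1.5, the eligibility limit in Table 2, it is 0.

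**Step 3: worked case (illustrative values).** Baseline bilirubin is 0.6 x ULN. At 24 hours ALT and AST are 4 x ULN and bilirubin is 2.2 x ULN. At 96 hours bilirubin is 1.3 x ULN, and ALT and AST are 2.5 x ULN. Transaminases are back to baseline by day 7, so bilirubin alone decides. There is no INR rise and there are no symptoms.

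| Rule | Test | Action |
|---|---|---|
| 15.2 | 1.3 > 0.6 | Discontinue from study |
| Table 14, stop row | 1.3 > 0.6 | Discontinue both drugs |
| Table 14, rechallenge row | 1.3 ≤ 1.5 and 2.5 ≤ 3 (Grade 1) | Restart AZD4573 at same dose |

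**Step 4: does anything break the tie?** Section 15.12.1 points back to Table 14 for timeframes and names no level. Section 17.1.10.9 speaks of resolution, also without a level. Footnote c to Table 14 says "Participants who are considered for rechallenge in the event of Grade 4 transaminase increases or PHL must discuss possible risk of hepatotoxicity", which shows that rechallenge after PHL is intended in principle. It would be equally true if rechallenge required a return to baseline, so it does not settle the level.

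**Step 5: study or treatment?** Section 15.2 discontinues the participant from the study. For bilirubin unresolved at the same 96 hours, Section 17.1.10.9 discontinues study treatment and keeps the participant on study for the 30-day and long-term visits. Both cannot be followed.

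**The case against.** The best defence is that a careful reader can still rank the rules. Section 15.2 is mandatory in tone, whereas Table 14 is titled as recommended modifications. Baseline is also the standard in Section 15.2, in the stop row and in the isolated Grade 3 bilirubin row, so the rechallenge row is the outlier. The sponsor is involved as well: Section 17.1.6 requires contact with the Medical Monitor if an event is unresolved at 96 hours, Section 8.2.6 makes PHL a serious adverse event, and Section 17.1.10.9 has PHL reviewed jointly. Appendix E, to which Table 14 refers for PHL, was not in the text available.

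Part of this stands. It makes baseline the sensible default, and it makes an unnoticed divergence less likely. It does not remove the contradiction. Both rows sit in the same table, so its title cannot rank one above the other. The Medical Monitor contact depends on the event being unresolved, which is the term left without a level.

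On follow-up, a reader might infer that Section 15.2 ends all observation. It does not: biochemistry continues, and Section 7.2 asks for the 30-day visit where possible and survival follow-up for all participants. What differs is mainly the long-term disease follow-up.

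A reader might also infer that the DLT count is faulty. Section 15.3 scores bilirubin as a DLT "where bilirubin does not return to meet initial eligibility criteria within 72 hours of onset or 96 hours of start of dosing", so the worked case is a stop without a PHL DLT. Its symptom criterion, "of any duration if associated with symptoms or signs of liver impairment", also needs raised bilirubin, whereas the Table 14 symptom row does not. A stopping rule broader than the DLT definition is an ordinary conservative choice, not an error. Nor does a stop after the fifth infusion clearly escape the dosing-delay criterion because the missed doses fall in Cycle 2. That criterion is most naturally read as requiring the toxicity, not the missed doses, to fall within the assessment period.

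**Conclusion.** The point holds in a narrow form. The rules are wrong as written for PHL with both ALT and AST at least 3 x ULN, bilirubin at least 2 x ULN, no INR rise and no symptoms, where bilirubin at 96 hours is above baseline but at or below 1.5 x ULN. It does not extend to PHL in general: with only one transaminase raised, or with symptoms or an INR rise, the rechallenge row does not apply. The separate disagreement between stopping treatment and leaving the study also holds.

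The size is qualitative: opposite instructions for each participant in the band. The protocol reports that biochemical changes meeting Hy's Law criteria have occurred with AZD4573, but gives no frequency from which to estimate how many participants fall there. Urgency is moderate. Recruitment has stopped (Section 4.1). Section 6.13 lets participants continue after data cut-off under this protocol and the Investigator's Brochure, while Section 15.7 points their investigators to the Brochure, so the protocol's rules carry less weight for them.

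The conclusion assumes no Gilbert's syndrome, Table 14's own Grade 1 limit, and that Appendix E sets no precedence.

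**What to change.** 1. Use one bilirubin recovery level for PHL in Section 15.2 and in both Table 14 rows. The default consistent with Section 15.2 and the stop row is baseline, which means deleting the Grade 1 alternative for bilirubin from the rechallenge row. If the sponsor intends Grade 1, change Section 15.2 and the stop row instead. The choice is a clinical one.
2. Give the same level wherever Sections 15.12.1 and 17.1.10.9 speak of resolution, and confirm that Appendix E agrees.
3. In Section 15.2, replace discontinuation from the study with permanent discontinuation from study treatment. Keep the biochemistry follow-up and the 30-day and long-term visits.

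The cost is a few aligned phrases. Choosing baseline means a few more permanent stops. Choosing Grade 1 means re-dosing some participants whom Section 15.2 now stops.
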